3.4.3 Rescue medications and treatment

Rescue treatment is defined as, after randomization, participant receives SCS for any reason, and/or are recommended for sinonasal surgery to relieve CRS symptoms.

The following rescue medication is recommended for worsening or uncontrolled severe CRS symptoms that results in the participant contacting the investigator who determines an initiation of rescue treatment is necessary any time during the study:

- A course of oral corticosteroids. Typical indications include persistent sinus infection after an initial course of antibiotics while starting another course of antibiotics, uncontrolled sinus inflammation, or a flare-up of asthma. The dose, duration of use, and rationale for the use of oral corticosteroid must be recorded.
- Sinonasal surgery as rescue treatment according to the investigator's recommendation. The type and rationale for sinonasal surgery must be recorded.

3.5 Methods and procedures

The study-required activities and assessments are detailed below and are presented in tabular form in Appendix 14.1.

3.5.1 Eligibility assessment

Participants are considered eligible for this study if they meet all the inclusion criteria and none of the exclusion criteria as defined in **Section 3.3**. The principal investigator or subinvestigator at each investigational site will determine participant eligibility based on the inclusion/exclusion criteria.

3.5.2 Screening visit and run-in stage

After providing written informed consent, participants who are qualified to participate in this study, have failed previous medical management and are no longer on oral or intranasal corticosteroids will have an initial Screening visit. Assessments at Screening will include demographics and medical history, a limited physical examination (head, neck, ear, nose, and throat) with vital signs, hematology and chemistry tests, SNOT-22 questionnaire, serum pregnancy test for women of childbearing potential, COVID-19 test, sinus CT (or within 1 month of Screening), nasal endoscopy, ocular examination (visual acuity [VA], IOP, and slit lamp), eligibility assessment, and concomitant medications/procedures.

Immediately following the initial Screening visit, participants will undergo a run-in period of 2-4 weeks. During this run-in period, if a patient requires rescue medication, he/she will not be enrolled into the study. In the event of difficulties in scheduling Day 1 visit (randomization), the run-in period can be extended up to day 35 with sponsor/medical monitor approval. If a participant fails the initial screening, they are permitted to be rescreened one time under a new participant ID.

Participants who fail screening due to administrative reasons (eg, visit window) or abnormal lab value(s) may be allowed to repeat certain screening assessment(s) and re-establish eligibility. To

minimize patient burden, the sinus CT, ocular exam and/or endoscopy do not need to be repeated for rescreened participants if done within the preceding month. Medical Monitor approval is required in such cases. Documentation of the decision and Medical Monitor approval will be filed in the participant's file.

Participants will be provided with saline and instructions for daily intranasal saline irrigation starting from the Screening visit throughout the study. Participants will be instructed to stop use of saline rinse approximately 24 hours prior to the scheduled sinus CT. Daily saline irrigation should then continue following the sinus CT. Daily saline irrigation procedures should adhere to the Investigator's prescribing information and local standards, as applicable. Beginning at least 14 days prior to LYR-210 administration/sham procedure on Treatment Day (Day 1), participants will record daily scores for each of the 4 cardinal symptoms (4CS) of CRS (nasal blockage/obstruction/ congestion, nasal discharge, facial pain/pressure, reduction/loss of sense of smell) on the electronic patient-reported outcomes (ePRO) questionnaire.

3.5.3 Day 1 visit, pretreatment

On Day 1, before randomization, participants will undergo the following assessments: urine pregnancy test for women of childbearing potential, COVID-19 test, eligibility assessment, nasal endoscopy, baseline ePRO questionnaires (4CS, SNOT-22, PGIS, WPAI-SHP SF-36v2, EQ-5D-5L, MOS Sleep R), current medication listing, and AE reporting. Additionally, the first 30 randomized participants will be selected to have blood drawn for baseline plasma PK testing.

3.5.4 Randomization and blinding

On Day 1, after confirmation of eligibility and baseline assessments, and before any treatment, participants will be randomized in a 2:1 ratio to receive LYR-210 treatment or control (sham procedure) with stratification based on region (North America vs Europe) and nasal polyp status (yes vs no). Randomization will be conducted using Interactive Response Technology (IRT) and treatment will be assigned according to a randomization scheme generated by an unblinded biostatistician. The person generating the randomization scheme will not be involved in the collection, review, and/or analysis of study data before database lock and unblinding of the database.

To maintain the participant blind to treatment assignment, each participant will wear an eye mask (ie, blindfold) and headphones at the time of the LYR-210 administration/sham procedure. Except for the cases of spontaneous matrix dislodgement, participants should remain blinded to their treatment assignment (LYR-210 or control) until the study is completed.

After Week 24, using IRT, control participants will be assigned to active treatment and treatment participants will be re-randomized 1:1 to either sham procedure or a second active treatment

procedure stratified by geographic region and nasal polyp status at baseline. Follow-up visits will continue through Week 52.

The sponsor will be blinded only to participants' initial study treatment assignments until database lock for the Week 24 primary analysis (initial randomized phase).

Due to the nature of the procedure, the treating investigator/surgeon will not be blinded to the treatment assignment. Efforts will be made to keep the study coordinator and other study staff blinded.

Breaking the blind to the participant is expressly forbidden except in the event of spontaneous dislodgment of LYR-210, or a medical emergency where the identity of the treatment assignment must be known to properly treat the participant. If breaking the blind is required because of a medical emergency, decision to unblind lies solely with the investigator. In all cases where the blind is broken to the participant, the investigator must record the date and reason for breaking the blind. The unblinding should be noted in the participant's eCRF.

3.5.5 Treatment procedure (active and sham)

On Day 1, after completing all required pretreatment assessments and randomization, participants will receive local anesthetic in the middle meatus and undergo a baseline nasal endoscopic assessment in preparation for the insertion procedure. Before the administration of the LYR-210 or sham procedure, participants will have nasal swabs collected for protein and cytology.

On Day 1, participants who are assigned to the active treatment arm will have the LYR-210 administered bilaterally into the middle meatus according to the sponsor's instructions for use. Participants who are assigned to the control arm, will undergo mock administration (ie, sham procedure)

After the procedure, all participants will be instructed to continue daily saline irrigation and completion of daily 4CS ePRO.

If the investigator is unable to administer LYR-210 bilaterally or perform sham procedure successfully into both middle meatuses of a participant, the investigator will remove any LYR-210 already administered and treat the participant with any appropriate therapy, if necessary. The participant will be considered a **treatment administration failure**. Treatment administration failure participants will be followed within 7 (±2) days by telephone for AE and concomitant medication assessments. Treatment administration failure participants may be replaced to ensure adequate study enrollment.

3.5.6 Telephone/virtual visits

Participants will receive telephone/virtual follow-ups at Weeks 4, 12, 28, and 36 to record AEs and concomitant medications/procedures that they have had since their last follow-up assessment. Participants will also complete 4CS, SNOT-22 and WPAI-SHP at these visits and women of childbearing potential will undergo a urine home pregnancy test.

The Week 52/EOS visit can be conducted either over the phone/virtual or as an office visit.

3.5.7 Clinic follow-up visits

All participants will return to clinic for the scheduled follow up assessments at Weeks 8, 16, 20, 32, 40, 44, and 48. The end of study visit at Week 52 can be conducted as an in-office visit or over the phone. Assessments at these visits include a urine pregnancy test for women of childbearing potential, COVID-19 test, nasal endoscopy, 4CS, SNOT-22, concomitant medications/procedures, and AEs. PGIS will also be assessed at Week 8 and 16 visits. Plasma for PK testing will be collected for the previously selected 30 participants. Ocular examinations are required at Weeks 8, 16, 32, 40, and 48.

At the Week 20 and Week 44 visits, after the visit assessments, all participants will undergo a LYR-210 removal or sham removal procedure. Participants who receive LYR-210 will have bilateral matrix removal using standard surgical tools. Control participants will undergo a sham removal procedure to remain blinded.

If **spontaneous dislodgement of LYR-210** occurs before the scheduled Week 20 or Week 44 visit in participants who receive LYR-210, participants are required to call the study clinic immediately to report the event. If a participant experiences dislodgement of 1 LYR-210 matrix, the participant will continue in the treatment phase. Any participant who undergoes a dual dislodgement is required to complete the assessments scheduled for the Week 20/ET visit, and subsequently the Week 24/End of Treatment Phase (EOTP) visit within 25-31 days of the ET visit. Participants with dual dislodgement can be re-randomized in the extension phase.

Opacification of ethmoid sinuses will be assessed by CT scans obtained during screening (or using a historical CT scan taken within 1 month of screening) and within 7-14 days after Week 20/ET visit, unless medically contraindicated. Participants will be instructed to stop use of saline rinse approximately 24 hours prior to the scheduled sinus CT. Daily saline irrigation should then continue following the sinus CT. If a participant is experiencing or recovering from a cold, acute exacerbation of nasal allergy, or URTI at the timing of follow up CT, the CT should be performed 4 weeks after resolution of the AE. If a participant requires SCS or sinonasal surgery as rescue treatment, the follow-up CT should be performed before receiving the rescue treatment.

3.5.8 End of treatment phase (Week 24)

All participants will undergo a Week 24 visit. If medically warranted per the treating physician's discretion (for example, needing sinonasal surgery as rescue treatment), early matrix removal

may be performed at an unscheduled **early treatment termination (ET)** visit. Any participant who undergoes an ET visit is required to complete the assessments scheduled for the Week 20/ET visit, and subsequently the Week 24/End of Treatment Phase (EOTP) visit within 25-31 days of the ET visit. ET participants are encouraged to continue completing ePRO assessments through Week 24.

Week 24/EOTP assessments include a urine pregnancy test for women of childbearing potential, COVID-19 test, hematology and chemistry tests, nasal endoscopy, ocular examination (IOP and slit lamp), all ePRO (4CS, SNOT-22, WPAI-SHP SF-36v2, EQ-5D-5L, PGIS, PGIC, MOS Sleep R), concomitant medications/procedures, nasal swab collection, and AEs.

Participants will also complete the End of Treatment (EOT) at this visit.

3.5.9 Safety extension treatment

After completing the Week 24 visit, participants who completed the 24-week treatment phase (including participants with dual dislodgement) will continue into the safety extension phase. In this phase, all sham participants will undergo treatment with LYR-210. Treatment participants will be re-randomized 1:1 to undergo either a sham procedure or a second LYR-210 treatment procedure. Extension participants will not be required to repeat the Screening/run-in phase or CT scans but will otherwise repeat all the study visits and assessments for the 24-week treatment phase (see safety extension schedule of assessments in **Appendix 14.1**). Participants in the safety extension phase will undergo a second removal procedure at Week 44 and complete follow-up visits at Weeks 48 and 52. If medically warranted per the treating physician's discretion, early matrix removal may be performed at an unscheduled ET visit. Any participant who undergoes an ET visit is required to complete the assessments scheduled for the Week 44/ET visit, and subsequently the Week 48/End of Safety Extension Phase (EOSEP) visit within 25-31 days of the ET visit. ET participants are encouraged to continue completing ePRO assessments through Week 52.

Week 52 is the EOS visit for all participants who did not have early termination. The Week 52/EOS visit can be conducted either over the phone/virtual or as a clinic visit. Assessments include final ePROs (4CS and SNOT-22), concomitant medications/procedures, and AEs.

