3.5.10 Discontinuation of Study Participants

Each subject is free to discontinue from the study at any time, for any reason, and without penalty or loss of benefit. Participation in the study treatment may be discontinued for any of the following reasons:

• Occurrence of any medical condition or circumstance that exposes the subject to substantial risk and/or does not allow the subject to adhere to the requirements of the protocol, including early removal of LYR-210

- Any serious AE (SAE, Section 7.2), clinically significant AE, severe laboratory abnormality, intercurrent illness, pregnancy, or other medical condition that indicates to the Investigator that continued participation is not in the best interest of the subject.
- Subject's decision to withdraw
- If deviations to the use of prohibited medications occur after randomization and study treatment, the Investigator in consultation with the Sponsor and Sponsor's medical monitor will decide on a case-by-case basis whether the subject may continue in the study based on the time the prohibited medication was administered and its pharmacology.
- Subject's failure to comply with protocol requirements or study related procedures.
- Termination of the study by the Sponsor or a regulatory authority that has provided approval to proceed.

Subjects who withdraw or are withdrawn from the study treatment will be requested to return to the clinic for the assessments and procedures scheduled for the end of treatment visit and the safety follow up visits (Section 3.5.9). The Investigator or study staff will document the reason(s) for subject discontinuation on the Case Report form (CRF) and notify the IRB/EC as required by their Institution's procedures.

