3.7.13 Sinonasal surgery (actual or planned) for CRS

For participants who have a surgery or have a scheduled date for sinonasal surgery as rescue for CRS, the reason (worsening signs and/or symptoms during the study), the date the surgery was indicated, expected or actual surgery date, and the type and outcome of surgery will be recorded in the eCRF. Types of sinonasal surgery include, but are not limited to, functional endoscopic sinus surgery (FESS), balloon sinuplasty, turbinate reduction, septoplasty or polypectomy, or any endoscopic procedure that results in sinonasal tissue removal.

If the surgery is to be performed during the study treatment period, the study treatment will be discontinued and all procedures/assessments for the ET and EOTP visits will be completed prior to the surgery. The participant will be discontinued from the study.

If the surgery is to be performed during the safety extension phase, the study treatment will be discontinued and all procedures/assessments for the ET and EOSEP visits will be completed prior to the surgery. The participant will be discontinued from the study.

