7.8 Exposure in utero

If a participant becomes pregnant during the treatment phase, the matrix will be removed (or sham removal) and the participant will continue study follow-up through Week 24. The participant will not continue to the safety extension phase. However, the investigator must continue to follow the participant until the completion of the pregnancy, including the outcome and the condition of the newborn at 8 weeks postpartum (if applicable).

If a participant becomes pregnant during the safety extension phase, the matrix will be removed (or sham removal) and the participant will continue study follow-up through Week 52. Additionally, the investigator must follow the participant for safety until the completion of the pregnancy, including the outcome and the condition of the newborn at 8 weeks postpartum (if applicable).

A pregnancy is not considered to be an AE or SAE; however, it must be reported within 24 hours of knowledge of the event. Sponsor or designee will then provide the Exposure In Utero (EIU) form to the investigator/site for completion and return.

The pregnancy should be followed until the outcome of the pregnancy, whenever possible. Once the outcome of the pregnancy is known, the EIU form should be completed and faxed/emailed to sponsor or designee. If the outcome of the pregnancy meets the criteria for immediate classification as an SAE (ie, postpartum complication, spontaneous abortion, stillbirth, neonatal death, or congenital anomaly), the investigator should follow the procedures for reporting an SAE.

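### SAP 3.1.2.2 and SAP 3.1 set conflicting cut-offs for Week 24 safety exams, and the literal 3.1.2.2 rule drops exams done on the day of extension assignment

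*Protocol*

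**What the plan says.** Protocol 3.5.8 schedules these safety exams at Week 24, among others: "hematology and chemistry tests, nasal endoscopy, ocular examination (IOP and slit lamp" and visual assessments as marked in Table 4. Participants who complete the treatment phase then move into the extension under Protocol 3.5.9. For the control arm, "In this phase, all sham participants will undergo treatment with LYR-210"; LYR-210 participants are re-randomized 1:1 to sham or a second LYR-210 placement.

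Table 5 note a makes extension Day 1 the same visit as Week 24. Note d places extension assignment and the procedure after the required Week 24 assessments are complete. The treatment-assignment row of Table 5 reserves re-randomization for the treatment group and describes the control group as assigned.

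The SAP gives two rules for which safety exams belong to the 24-week analysis:

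- SAP 3.1 opens with a general cut-off before the re-randomization date. It then makes a specific provision for laboratory tests, nasal endoscopy, vital signs and ophthalmologic assessments, which count up to and including the day of successful extension insertion.
- SAP 3.1.2.2, which introduces the safety windows in Tables 1f to 1h, says that for participants entering the extension every day must fall before the re-randomization date. It does not repeat the provision in SAP 3.1.

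**The concern.** The two rules disagree about the normal case. A participant who attends Week 24 on schedule, has the exams, and is assigned and treated at that visit has exam dates equal to the assignment date. SAP 3.1.2.2 excludes those exams and SAP 3.1 includes them.

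At stake are the laboratory, IOP, cataract and endoscopic safety endpoints through Week 24 (SAP 2.3.5). Laboratory tests and slit-lamp have no other scheduled post-baseline time point in the treatment phase. Protocol 9.3.5 does not impute missing safety data, so a dropped exam stays missing. SAP 3.1.5 generally bases percentages on participants with non-missing data, so the denominators would shrink as well.

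**Working it through.** No figure in the plan needs to be reproduced here. The check compares dates and counts scheduled exams.

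**Step 1: do the windows themselves keep the exam?** Table 4 puts Week 20 at Day 141 ± 3 and Week 24 at 25 to 31 days later.

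- Earliest Week 24 visit: 141 − 3 + 25 = Day 163.
- Latest Week 24 visit: 141 + 3 + 31 = Day 175.

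The Week 24 windows are Day 85 to 210 for laboratory and slit-lamp (SAP Table 1f) and Day 148 to 210 for IOP and endoscopy (Tables 1g and 1h). Days 163 to 175 lie inside all of them. Only the date cut-off can remove an on-time exam.

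**Step 2: apply each cut-off to a same-day exam.** Let the exam, the extension assignment and the insertion all fall on day D.

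- SAP 3.1.2.2 needs exam day < D. The exam is on D, so it is dropped.
- SAP 3.1 needs exam day ≤ D. The exam is on D, so it is kept.

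**Step 3: count what is lost per affected participant** (Protocol Table 4, SAP 3.6.2 and SAP Tables 1f to 1h).

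| Exam | Scheduled post-baseline weeks | Lost under literal 3.1.2.2 |
|---|---|---|
| Laboratory | 24 | 1 of 1 |
| Slit-lamp | 24 | 1 of 1 |
| IOP | 8, 16, 24 | 1 of 3 |
| Nasal endoscopy | 8, 16, 20, 24 | 1 of 4 |

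SAP 3.6.5 also lists cataract summaries at Weeks 8 and 16. However, the Table 4 footnote limits those ocular visits to IOP, and SAP Table 1f has only a Week 24 window, so slit-lamp is counted once. Vital signs are named in SAP 3.1 but scheduled only at Screening, so nothing is lost there.

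**Step 4: how many participants?** The number is 180 × (fraction continuing) × (fraction with the exam on the assignment day). The documents give neither fraction.

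- Same-day fraction 0: nobody is affected.
- Same-day fraction 1 and everyone continues: 180.
- Same-day fraction 1 and an assumed 80% continue: 180 × 0.8 = 144.

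The range is therefore 0 to 180, and it can differ by exam. The ocular exam may be done up to two weeks before the visit, and an ocular exam done earlier survives both rules.

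**Step 5: does the cut-off date exist in both arms?** Read against Table 5, a re-randomization date exists only for the LYR-210 arm (120 of 180 planned). The 60 sham participants have an extension assignment date from the IRT and an insertion date, but no re-randomization in the literal sense.

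**The case against.** **The intent is clear.** SAP 3.1 names the exam types and expressly includes the insertion day. The sentence in 3.1.2.2 repeats the one in the efficacy section, 3.1.2.1, and looks carried over. SAP 3.6.2 and 3.6.5 call for Week 24 laboratory and ophthalmologic summaries, which the literal rule would strip of same-day exams. Safety comparisons carry no formal tests. All of this stands and makes serious data loss unlikely. It does not remove the conflict, because 3.1.2.2 is the section that governs the safety windows and a programmer following it would apply the stricter rule.

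**The loss falls on LYR-210 only.** A reader might infer this from the Table 5 wording. The documents do not support it well: 3.1.2.2 speaks of all subjects entering the extension, and controls are also assigned through the IRT, so the natural reading covers both arms. What remains is that the term needs replacing.

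**Extension LYR-210 is placed with no safety check.** A reader might infer this from "Extension participants will not be required to repeat the Screening/run-in phase or CT scans", because the initial Day 1 visit includes "urine pregnancy test for women of childbearing potential, COVID-19 test, eligibility assessment, nasal endoscopy" and the readable part of Table 5 shows no eligibility row. The documents do not establish an omission:

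- Protocol 3.5.9 says the other visits and assessments are repeated, which can be read to include the Day 1 eligibility assessment.
- The public copy of Table 5 is visibly damaged (the adverse-event footnote m has no readable row, and other markers are shifted), and Appendices 14.4 to 14.14 are redacted. A missing row is weak evidence.
- Note d puts the Week 24 exams before placement, so an ocular exam scheduled late delays placement rather than following it.
- Protocol 3.5.10 states "Participation in the study treatment may be discontinued for any of the following reasons" and lists substantial risk and clinically significant adverse events. Protocol 7.8 bars pregnant participants: "The participant will not continue to the safety extension phase".

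A fixed bar on every entry exclusion would also give no deferral for transient findings such as purulence, and it would remove participants with new findings from the extension safety sample.

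**Conclusion.** The SAP text is wrong as written. Two explicit rules give opposite answers for a Week 24 safety exam done on the day of extension assignment, which is the scheduled arrangement. For each affected participant the literal 3.1.2.2 rule removes the only scheduled post-baseline laboratory and slit-lamp results, one of three IOP readings and one of four endoscopies. The number affected lies between 0 and 180 and cannot be narrowed from the documents.

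This rests on reading 3.1.2.2 literally and on Table 5 notes a and d. An unscheduled exam inside the window could stand in for a dropped one under SAP 3.1.2, so the loss is of scheduled data and not necessarily of all data. The point concerns safety exams only. The efficacy windows in SAP 3.1.2.1 carry the same cut-off, but SAP 3.1 makes no contrary provision for efficacy data, so this particular conflict does not arise there.

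The absence of a stated eligibility check before extension placement is not shown to be an error.

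**What to change.** In SAP 3.1.2.2, replace the re-randomization cut-off with the one in SAP 3.1. For participants in either arm who enter the extension, laboratory, endoscopy and ophthalmologic results count if collected up to and on the date of extension insertion, before the procedure. This also gives sham participants a defined date.

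The cost is one sentence, with no new data and no change to visits. It should be made before the Week 24 database lock. If the SAP is already final, SAP section 1 provides for recording such a change in the clinical study report.

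Optional clarification, not a correction: state in Protocol 3.5.9 that the investigator reviews the Week 24 endoscopic and ocular findings before extension placement, with deferral and re-check for transient findings. This uses exams already scheduled.
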